2 LIST OF ABBREVIATIONS AND DEFINITIONS OF TERMS

Abbreviation	Term
AE	adverse event
AHI	apnea hypopnea index
ANOVA	analysis of variance
ATC	anatomical therapeutic class
BLQ	below the limit of quantification
BMI	body mass index
CI	confidence interval
COPD	chronic obstructive pulmonary disease
CRF	case report form
CTCAE	Common Terminology Criteria for Adverse Events
CV	coefficient of variation
ECG	electrocardiogram
EOS	end of study
E-R	exposure response
GOLD	Global Initiative for Chronic Obstructive Lung Disease
MedDRA	Medical Dictionary for Regulatory Activities
NREM	non rapid eye movement
ODI	oxygen desaturation index
OSA	obstructive sleep apnea
PD	pharmacodynamic(s)
PK	pharmacokinetic(s)
PSG	polysomnography
REM	rapid eye movement
SAE	serious adverse event
SAP	statistical analysis plan
SD	standard deviation
SI	Système International
SOC	system organ class

Abbreviation	Term
SpO ₂	mean oxygen saturation
TEAE	treatment-emergent adverse event
TLG	tables, listings, and graphs
TST	total sleep time
WHO	World Health Organization

3 INTRODUCTION

The purpose of this statistical analysis plan (SAP) is to describe the procedures and the statistical methods that will be used to analyze and report results for Eisai Protocol E2006-A001-113.

3.1 Study Objectives

3.1.1 Primary Objectives

OSA Cohort:

- Using polysomnography (PSG), determine whether lemborexant increases the apnea hypopnea index (AHI) on Day 8 of treatment in adult and elderly subjects (adults ≥ 45 to <65 years; elderly ≥ 65 to 90 years) with moderate to severe obstructive sleep apnea (OSA) compared with placebo

COPD Cohort:

- Using pulse oximetry, determine whether lemborexant decreases mean oxygen saturation (SpO₂) during TST on Day 8 of treatment in adult and elderly subjects with moderate to severe chronic obstructive pulmonary disease (COPD) compared with placebo

3.1.2 Secondary Objectives

OSA Cohort:

- Using PSG, determine whether lemborexant increases the AHI on Day 1 of treatment compared with placebo
- Using pulse oximetry, determine whether lemborexant decreases the mean oxygen saturation (SpO₂) during total sleep time (TST) on Days 1 and 8 of treatment compared with placebo
- Using pulse oximetry, determine whether lemborexant increases the percentage of TST during which the SpO₂ is $<90\%$, $<85\%$, and $<80\%$ on Days 1 and 8 of treatment compared with placebo
- Using pulse oximetry, determine whether lemborexant decreases the mean oxygen desaturation index (ODI) during TST on Days 1 and 8 of treatment compared with placebo
- Using pulse oximetry, determine whether lemborexant decreases the absolute number of desaturations ($\geq 3\%$ reduction from Baseline SpO₂) during TST on Days 1 and 8 of treatment compared with placebo
- Evaluate safety and tolerability of lemborexant compared with placebo

COPD Cohort:

- Using pulse oximetry, determine whether lemborexant decreases mean SpO₂ during TST on Day 1 of treatment compared with placebo
- Using PSG, determine whether lemborexant increases the AHI on Days 1 and 8 of treatment compared with placebo
- Using pulse oximetry, determine whether lemborexant increases the percentage of TST during which the SpO₂ is <90%, <85%, and <80% on Days 1 and 8 of treatment compared with placebo
- Using pulse oximetry, determine whether lemborexant decreases the mean oxygen desaturation index (ODI) on Days 1 and 8 of treatment compared with placebo
- Using pulse oximetry, determine whether lemborexant decreases the absolute number of desaturations ($\geq 3\%$ reduction from Baseline SpO₂) on Days 1 and 8 of treatment compared with placebo
- Evaluate safety and tolerability of lemborexant compared with placebo

3.1.3 Exploratory Objectives

OSA and COPD Cohorts:

Explore the effects of lemborexant compared with placebo on the following for Days 1 and 8 of treatment:

- The mean SpO₂ during rapid eye movement (REM) sleep, non-REM (NREM) sleep, and wake
- The mean ODI during REM sleep and NREM sleep
- The absolute number of desaturations during REM sleep and NREM sleep
- AHI during REM and NREM sleep
- Determine whether lemborexant increases the AHI, and decreases the mean SpO₂ during TST separately for adult and elderly subjects
- Determine whether lemborexant increases the mean ODI, and increases the absolute number of desaturations, during TST separately for adult and elderly subjects

In addition, explore the following pharmacokinetic (PK) endpoints for both OSA and COPD Cohorts:

- Plasma concentrations of lemborexant and its metabolites (M4, M9, and M10)
- Exposure-response (E-R) relationships between lemborexant concentrations and pharmacodynamic (PD) variables, including but not limited to respiratory safety variables (AHI, mean SpO₂ during TST, percentage of TST in which SpO₂ is <90%, <85%, and <80%, means ODI, and absolute number of desaturations).

3.2 Overall Study Design and Plan

In the OSA and COPD Cohorts, this will be a randomized, double-blind, placebo-controlled, 2-period crossover study. There will be 2 phases, Prerandomization and Randomization. The Prerandomization Phase will last up to 21 days and will consist of the Screening Period and Baseline Period. The Randomization Phase will comprise 2 Treatment Periods, each of 8 days duration, separated by a washout interval of at least 14 days, and a Follow-Up Period of 14 days. Twenty-eight days after the final study dose, there will be an end of study (EOS) Visit.

4 DETERMINATION OF SAMPLE SIZE

OSA Cohort:

A mean difference between treatments in AHI >5 is considered clinically meaningful in studies of the respiratory safety of sleep agents in OSA (Kruger, et al., 2007, Sun, et al., 2016). The within-subject variance is assumed to be 25.34 for AHI for adult subjects (Sun, et al., 2016) and 30.41 for AHI for elderly subjects (where the elderly within-subject variance is estimated from adult data +20%, Mitterling, et al, 2015; Lee, et al, 2016). Assuming the true difference in AHI (lemborexant –placebo) on Day 8 is as high as 1.5, a total of 30 subjects completing the study (20 adult, 10 elderly), provides 82% power that the upper bound of the 90% CI for the treatment difference in AHI (lemborexant – placebo) on Day 8 would be less than 5.

Description	Combined within-subject variance of AHI	Adult N	Elderly N	Total N	Total Power (%)
80% overall power with 20 adult subjects	26.96	20	10	30	82
85% overall power with 20 adult subjects	27.38	20	14	34	86
80% overall power with 20 elderly subjects	28.54	12	20	32	82
85% overall power with 20 elderly subjects	28.16	16	20	36	86
Equal number of subjects	27.875	20	20	40	90

COPD Cohort:

A 2% decrease in mean SpO₂ during TST is considered a clinically meaningful change. For the primary hypothesis (mean SpO₂ during TST on Day 8), assuming a true within subject variance of 1.07% for mean SpO₂, a significance level of 0.05, and a true difference of -1 percent point, a total of 30 subjects completing the crossover study provides 99% power that the lower bound of the 90% confidence interval for the mean difference in mean SpO₂ (LEM- placebo) on Day 8 would be greater than -2 percent points. The true difference could be as low as -1.23% and the study still would have had 80% power to support the hypothesis.

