**COPD Cohort:**

A 2% decrease in mean SpO2 during TST is considered a clinically meaningful change. For the primary hypothesis (mean SpO2 during TST on Day 8), assuming a true within subject variance of 1.07% for mean SpO2, a total of 30 subjects completing the crossover study, and significance level alpha 0.05, there is 0.95 probability that the lower bound of the 90% confidence interval (CI) for the true mean difference in mean SpO2 (LEM- placebo) on Day 8 would be greater than 2 percent points, if the true difference is 1 percent point. The true difference could be as low as 1.23% and the study still would have had 80% power to support the hypothesis.

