###### Analysis for the Primary Endpoint

**OSA Cohort:** Mean AHI will be analyzed on the PD analysis set using repeated measures ANOVA, for Day 8 of each treatment period. The model will include fixed effects for age group, sequence, period, and treatment, and a random effect for subject within sequence. The following will be presented: least square (LS) means, difference in LS mean of lemborexant 10 mg compared to placebo, a 2-sided 90% CI (equivalent to a 1-sided upper 95% CI) for the true mean difference (lemborexant – placebo) in AHI. If the upper bound of the 1-sided 95% CI of the treatment difference of AHI is less than 5, this will provide evidence that the given dose of lemborexant does not result in a clinically significant increase in AHI with moderate to severe OSA compared with placebo. Further details will be provided in the statistical analysis plan (revised per Amendment 01).

Plots of AHI and SpO2 treatment difference data (both individual and LS Mean) will be used to explore the results.

**COPD Cohort:** Mean SpO2 will be analyzed on the PD analysis set using repeated measures ANOVA, of values on Day 1 of each treatment for subjects in the PD analysis set. The model will include fixed effects for sequence, period, and treatment, and a random effect for subject within sequence. The following will be presented: LS means, difference in LS mean of lemborexant 10 mg compared to placebo, a 2-sided 90% CI (equivalent to a 1-sided lower 95% CI) for the true mean difference (lemborexant – placebo) in SpO2. If the lower bound of the 1-sided 95% CI of the treatment difference of SpO2 is greater than -2 (for active – placebo), this will provide evidence that the given dose of lemborexant does not result in a clinically significant decrease in SpO2 compared to placebo. Further details will be provided in the statistical analysis plan (revised per Amendment 01).

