### **COPD Cohort:**

A 2% decrease in mean SpO2 during TST is considered a clinically meaningful change. For the primary hypothesis (mean SpO2 during TST on Day 8), assuming a true within subject variance of 1.07% for mean SpO2, a total of 30 subjects completing the crossover study, and significance level alpha 0.05, there is 0.95 probability that the lower bound of the 90% confidence interval for the true mean difference in mean SpO2 (LEM- placebo) on Day 8 would be greater than 2 percent points, if the true difference is 1 percent point. The true difference could be as low as 1.23% and the study still would have had 80% power to support the hypothesis.

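### COPD power figures do not follow from the stated 90% CI and differ between protocol (0.95) and SAP (99%); the 90% CI gives about 98% at -1 and 80% at -1.32, not -1.23

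*SAP*

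**What the plan says.** SAP section 4 (COPD Cohort) assumes "a significance level of 0.05, and a true difference of -1 percent point" and a within-subject variance printed as 1.07%. It states that "a total of 30 subjects completing the crossover study provides 99% power that the lower bound of the 90% confidence interval" for lemborexant minus placebo lies above -2 points. It then adds: "The true difference could be as low as -1.23% and the study still would have had 80% power to support the hypothesis".

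Protocol section 9.7.2 (COPD Cohort) and the matching synopsis paragraph use the same variance, number of completers, alpha, interval, margin and size of true difference. There, however, "there is 0.95 probability that the lower bound of the 90% confidence interval" clears the margin. The threshold is printed without minus signs: the bound "on Day 8 would be greater than 2 percent points, if the true difference is 1 percent point". The follow-on sentence is "The true difference could be as low as 1.23% and the study still would have had 80% power to support the hypothesis".

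The analysis sections (protocol synopsis, protocol 9.7.1.7.2, SAP 5.5.1) specify a two-sided 90% CI, equivalent to a one-sided 95% bound. They give the rule with the correct sign: lemborexant passes if the lower bound "is greater than -2 (for active – placebo), this will provide evidence". SAP section 7 lists no changes to the planned analyses.

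**The concern.** One set of inputs should give one power figure, and the two documents give two. No modelling is needed to see that conflict, and neither document explains it.

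Each document's pair of figures (power at 1 point, and the difference at which power is 80%) should also be reproducible from the interval it names. If not, the stated CI level, the variance or the power is wrong, and the reader cannot tell which. The study is meant to satisfy a postmarketing requirement (protocol 7.3), and this paragraph is the numerical basis for the size of the COPD cohort. Anyone rechecking it will find that it does not reproduce.

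**Working it through.** **Inputs.** Within-subject variance 1.07, N = 30 completers, margin -2, true difference -1 or -1.23, two-sided 90% CI (one-sided alpha 0.05): SAP section 4 and protocol 9.7.2.

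**Formula.** For a 2×2 crossover, SE = √(2 × variance / N), df = N − 2, noncentrality = (margin − true difference)/SE with both taken as absolute sizes. Power is the probability that a noncentral t variable exceeds the critical t value.

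**Check of the method on the OSA cohort.** SAP section 4 says the design "provides 82% power that the upper bound of the 90% CI for the treatment difference in AHI" stays below 5.
- SE = √(2 × 26.96/30) = 1.341; noncentrality = (5 − 1.5)/1.341 = 2.611; df = 28.
- 90% CI (critical t 1.701): 81.6%, against 82% stated.
- 95% CI (critical t 2.048): 71.2%.

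The other four OSA rows behave the same way. With a 90% CI they give 85.4, 82.0, 86.4 and 89.7%, against 86, 82, 86 and 90% stated. With a 95% CI all five rows lie between 71.2 and 82.4%. So the OSA figures were computed with the 90% CI and this formula.

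**COPD.** SE = √(2 × 1.07/30) = 0.2671; df = 28.
- At -1: noncentrality = 1/0.2671 = 3.744.
- At -1.23: noncentrality = 0.77/0.2671 = 2.883.

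| | 90% CI (stated) | 95% CI | Protocol | SAP |
|---|---|---|---|---|
| Power at -1 | 97.8% | 95.1% | 95% | 99% |
| Power at -1.23 | 87.8% | 79.5% | 80% | 80% |
| Difference with 80% power | -1.32 | -1.225 | 1.23 | -1.23 |

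The normal approximation with the 90% CI gives 98.2% at -1, 89.2% at -1.23, and 80% at -1.34.

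**Reading the table.** Both protocol figures match the 95% CI column. The SAP's 99% is close to the 90% CI column, while its -1.23 belongs to the 95% CI column.

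**Can one assumption rescue the SAP pair?**
- Keep variance 1.07 and choose alpha to give 99% at -1: 80% power then falls at -1.40.
- Keep the 90% CI and choose the variance to give 80% at -1.23: power at -1 is then 94.3%.
- Keep the 90% CI and choose the variance to give 99% at -1: 80% power then falls at -1.37.
- Read 1.07 as an SD with a 90% CI: 97.0% at -1, and 80% at -1.296.

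None gives 99% together with -1.23.

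**Unit of 1.07.** Read as an SD with a 95% CI, it gives 93.7% at -1 and 80% at -1.198, which misses the protocol pair. Read as a variance, it reproduces that pair. It is therefore a variance, in squared percentage points.

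**Completers needed for 99% at -1 with a 90% CI.** N = 34 gives 98.8% and N = 36 gives 99.1%.

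**The case against.** Both documents also print a significance level of 0.05 without saying whether it is one- or two-sided. Read as two-sided, it yields both protocol figures, so the protocol pair is internally coherent and the fault there can be described as one unstated sidedness that clashes with the 90% CI in the same sentence. That is a fair account of the origin, but it does not remove the error, because the sentence names the 90% CI and so does every analysis section.

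A second coherent repair exists on paper: keep 0.95 and -1.23 and name a 95% CI. The OSA check shows only how the OSA figures were calculated, not what was intended for COPD. Yet that repair would make the COPD power paragraph disagree with the COPD decision rule in the protocol synopsis, protocol 9.7.1.7.2 and SAP 5.5.1. Correcting the power figures is the consistent choice.

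Some of the objection stands. The SAP's 99% taken alone is only about 1 point high; the clear errors are the protocol's 0.95 and the shared 1.23. Those two understate the design's power, so they do not mislead in the unsafe direction. The missing minus signs and the unit of the variance are editorial, and the intended direction is clear from the analysis sections.

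**Conclusion.** The point holds. Under the stated two-sided 90% CI with 30 completers and variance 1.07:
- power at -1 is about 98%; the protocol's 95% is 2.8 points low and the SAP's 99% about 1 point high;
- power at -1.23 is 87.8%, not 80%;
- 80% power is reached at -1.32, not -1.23.

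This rests on the standard crossover variance formula with 28 degrees of freedom and on reading 1.07 as a variance. Both are supported by reproducing the OSA figures and the protocol's own COPD pair. Using the normal approximation instead of t moves the results by about 1.4 points of power at most and does not change the conclusion.

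The adequacy of N = 30, the margin, the interval and the decision rule are unaffected. This is a documentation error that should be corrected. It does not threaten the analysis.

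**What to change.** Keep the two-sided 90% CI. In SAP section 4, protocol section 9.7.2 and the protocol synopsis, replace the COPD power sentences with wording such as: 30 completers give about 98% power that the lower bound of the two-sided 90% CI for lemborexant minus placebo exceeds -2 percentage points if the true difference is -1; power is 80% if the true difference is -1.32.

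In the same edit, state the significance level as one-sided 0.05, restore the minus signs in the two protocol paragraphs, and give 1.07 as a variance in squared percentage points.

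The cost is a text correction in three places. Two of them are in the protocol, where section 11.1 requires a written amendment or administrative change, so they can go in with the next one. The SAP can be corrected at once, with a note that its figures replace those in the protocol. Sample size, CI level, margin and decision rule do not change.

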5 STATISTICAL METHODS

All descriptive statistics for continuous variables will be reported using mean, standard deviation (SD), median, minimum and maximum. Categorical variables will be summarized as number (percentage) of subjects. All analyses will be performed separately for OSA and COPD cohorts.

5.1 Study Endpoints

5.1.1 Efficacy Endpoints

Not applicable.

5.1.2 Safety Endpoints

OSA AND COPD COHORTS

Safety assessments will be based on medical review of adverse event reports and the results of vital sign measurements, electrocardiograms, and clinical laboratory tests separately for each cohort.

5.1.3 Pharmacokinetic (PK) Endpoints

OSA AND COPD COHORTS

Lemborexant plasma concentrations at all days assessed for separately both cohorts

5.1.4 Pharmacodynamic (PD) Endpoints

PRIMARY ENDPOINT (OSA COHORT)

- AHI on Day 8 of treatment

SECONDARY ENDPOINTS (OSA COHORT)

- AHI on Day 1 of treatment
- Mean SpO₂ during TST on Day 1 and Day 8 of treatment

- The percentage of TST during which the SpO₂ is <90%, <85% and <80% on Day 1 and Day 8 in of treatment
- Mean oxygen desaturation index (ODI) on Days 1 and 8 of treatment
- Absolute number of desaturations ($\geq 3\%$ reduction from Baseline SpO₂) on Days 1 and 8 of treatment

PRIMARY ENDPOINT (COPD COHORT)

- Mean SpO₂ during TST on Day 8 of treatment

SECONDARY ENDPOINTS (COPD COHORT)

- Mean SpO₂ during TST on Day 1 of treatment
- AHI on Day 1 and Day 8 of treatment
- The percentage of TST during which the SpO₂ is <90%, <85% and <80% on Day 1 and Day 8 of treatment
- Mean oxygen desaturation index (ODI) on Days 1 and 8 of treatment
- Absolute number of desaturations ($\geq 3\%$ reduction from Baseline SpO₂) on Days 1 and 8 of treatment

EXPLORATORY ENDPOINTS (OSA AND COPD COHORTS)

- Mean SpO₂ during REM sleep, NREM and wake on Day 1 (and Day 8 for OSA Cohort) of treatment separately for each cohort
- AHI during REM and NREM sleep on Day 1 and Day 8 of treatment separately for each cohort
- AHI separately for adult and elderly subjects at all days assessed separately for each cohort
- Mean SpO₂ during TST separately for adult and elderly subjects at all days assessed separately for each cohort

5.2 Study Subjects

5.2.1 Definitions of Analysis Sets

Enrolled subjects will be defined as all subjects who provided informed consent. The two cohorts will be treated separately for all summaries and analyses. For the purposes of analysis the following analysis sets have been identified separately for each cohort:

- The Safety Analysis Set for each cohort is the group of subjects who received at least 1 dose of study drug and had at least 1 postdose safety assessment.

- The PK Analysis Set for each cohort is the group of subjects who received at least 1 dose of lemborexant and had at least 1 quantifiable plasma concentration after dosing with lemborexant.
- The Pharmacodynamic Analysis Set for each cohort is the group of subjects who had sufficient PD data to derive at least 1 PD parameter.

5.2.2 Subject Disposition

Reasons for screening failure will be summarized.

The number and percentage of subjects who completed the study will be summarized by treatment group and by sequence, and the number who discontinued prematurely will be summarized by reason for discontinuation by treatment group and by sequence.

5.2.3 Protocol Deviations

Major protocol deviations will be presented as a listing.

5.2.4 Demographic and Other Baseline Characteristics

Demographic and other baseline characteristics for the Safety Analysis Set will be summarized for each sequence and for all study drug groups combined using descriptive statistics. Continuous demographic and baseline variables include age, height, BMI, and weight variables; categorical variables include sex, age group (adults ≥ 45 to < 65 years; elderly ≥ 65 to 90 years), race, and ethnicity.

MEDICAL HISTORY

A subject data listing of medical and surgical history will be provided.

5.2.5 Prior and Concomitant Therapy

All investigator terms for medications recorded in the CRF will be coded to an 11-digit code using the World Health Organization Drug Dictionary (WHO DD) (March 2019 or later). The number (percentage) of subjects who took prior and concomitant medications will be summarized on the Safety Analysis Set by Anatomical Therapeutic Chemical (ATC) class, and WHO DD preferred term. Prior medications will be defined as medications that stopped before the first dose of study drug. Concomitant medications are defined as medications that (1) started before the first dose of study drug and are continuing at the time of the first dose of study drug, or (2) started on or after the date of the first dose of study drug to the last dose day plus 14 days. A concomitant medication in Treatment Period 1 is counted up to predosing of Treatment Period 2; a concomitant medication in Treatment Period 2 is counted up to the final study visit.

All medications will be presented in subject data listings.

5.2.6 Treatment Compliance

Compliance for the both the OSA and COPD cohorts for each study drug will be calculated on the basis of the number of tablets dispensed, lost and returned, for all randomized subjects.

Compliance = $\frac{\text{Number of tablets dispensed} - \text{number of tablets returned or lost}}{\text{Number of tablets expected to be taken by the subject for the treatment period}} \times 100$

If subject's treatment period was extended for any reason then the number of tablets expected to be taken will be increased appropriately. Summaries will provide descriptive summary statistics and number (percentage) of subjects using the categories <80%, $\geq 80\%$ to $\leq 100\%$, $>100\%$ to $\leq 120\%$, and $> 120\%$ for each treatment group.

